## 9. Research methods

### 9.1. Study design

This qualitative study will employ a multiple-case study design using document analysis of clinical guidelines combined with qualitative interviews with key informants from the organizations/entities that produce guidelines in these specific countries as well as representatives from national competent authorities. Case study is a research design that has been widely used in social science research. In this study, we use a sub-type that is a multi-case design - in contrast to a single case design - which includes multiple cases selected according to a case selection strategy that aligns with the aims and objectives of the research. This study employs a diverse case selection strategy which is characterized by the selection of a set of cases intended to represent the full range of values along at least two dimensions (12). In this study the two dimensions are the five RMMs/TAs and the six countries outlined above. The purpose of selection strategy is to represent a maximum range of geographical diversity across EU members countries as well as maximum range of diversity of stakeholders across therapeutic areas that may be subject to RMMs. By contrasting and comparing the cases in the multi-case design, we learn about commonalities and variations. We also illuminate the potential reasons for these variations. The diverse-case selection strategy enables an in-depth of understanding of RMM implementation including its variation across the EU, which, in turn, allows for the identification of problems to deal with through research or regulatory intervention.

The combination of document analysis followed by semi-structured interviews utilizes the capacity of qualitative interviewing to explore subjective, non-observable dimensions of social relations or work processes to supplement and extend understanding of the results from preceding document analysis (13). The use of two sources of data also allows an ongoing validity assessment based on the convergence of information from the two sources.

Whereas document analysis can capture whether and how regulatory RMMs are incorporated into clinical guidelines, the key informant interviews allow researchers to explore the revision processes that guidelines undergo as well as the perceived roles and responsibilities of the specific organization. The multiple case studies are descriptive in scope and provide means for initial exploration and the identification and characterization of differences between cases (14), such as differences between

countries and therapeutic areas, including enablers and barriers for updating and adoption of guidelines in clinical practice.

The study is framed in terms of networked risk governance as this conceptual framework provides a focus on the level of organizations, their guideline developing practices and the network dynamics of organizations cooperating across national and regional boundaries and health systems (14-16).

The methodology involves three components which will be divided over three work packages (WP):

### **WP1. Mapping of organisations**

We will undertake a mapping exercise to identify and describe the relevant organisations/entities/national group(s) of experts issuing and updating clinical guidelines. Identification of organizations/entities/national group(s), hereafter called “entities”, will be identified by the national teams and will occur through five case studies. The five case studies (see section 7) represent a selection of medicinal products that are prescribed and dispensed by a broad range of health care professionals, from primary and secondary care as well as nurses and pharmacists. It is therefore to be expected that the case studies will provide a clear overview of RMM uptake in clinical guidelines for each country. An overview of entities that are involved issuing and updating clinical guidelines for each country will be produced. Clinical guidelines are defined as guidelines that summarise current medical knowledge and provide evidence-based treatment recommendations for specific therapeutic areas. This does not include drug monographs or drug information that is copied directly from the regulatory source (product information/label) without any clinical context or where no editing processes are applied (standards, website such as [Farmacotherapeutisch Kompas](#) (NL) and [pro.medicin.dk – information om medicin](#) (DK)).

In each country, the mapping proceeds by the following steps: 1) identification, 2) assessment of eligibility, and 3) description. The first step is identifying entities, extracting key information that allows for assessment of eligibility (WP1). In case of eligibility, these will proceed to WP2 and WP3 (see figure 3).

[figure not shown]

Figure 3. Process overview for mapping of entities that issue/update clinical guidelines and assessment of eligibility of clinical guidelines and key informants for inclusion in WP2 and WP3.

First, entities will be identified using existing lists and registers, such as the register of officially recognized professional bodies or list of participants for public hearings on clinical guidelines. The information received from the MS will serve as a starting point (see EMA request for information (, Appendix III, page 35). Multiple lists will be consolidated and supplemented through web-search for clinical guidelines, through review of publications of clinical guidelines, including in national clinical journals, and their authors as well as existing own network of health care professionals.

The mapping exercise will involve an iterative approach to searching a range of available online sources for validation purposes, applying both entity-based searchers as well as guidelines-based search (see domain specific query in WP2) as the latter might not always be captured through entity search. When necessary, we will request relevant clinical guidelines from the identified entities. An iterative approach is necessary to ensure that all stakeholders issuing clinical guidance are included, and not only formally established bodies or professional associations. This includes a snowballing approach where identified entities will be asked to provide information on other entities that produce clinical guidelines in their country. In case material is unavailable or ambiguous, follow-up communication with a stakeholder will be taken (by email or telephone).

Secondly, identified organizations will be screened for eligibility (see figure 3). An example of potential inclusion and exclusion criteria has been provided below in Table 2 which will align with the tender specification of identifying “Key bodies and organisations responsible for issuing clinical guidelines for specific therapeutic areas, including national guideline committees and any other responsible bodies at local, national or European level”. We define trade unions as organisation of workers intent on "maintaining or improving the conditions of their employment. Their focus is mainly on wages and employee benefits. We defined accreditation bodies as authoritative bodies that give formal recognition of the competence of a certification body to provide certification services against a specified standard. For both we do not consider it likely that these issue clinical guidelines, and these are therefore excluded. Local level guidelines, such as single hospital-based guidelines will not be included. Only when no national or regional level guidelines are available, will we proceed with identifying and screening on the supranational level, which could be applicable for countries with lower number of inhabitants. In interviews in WP3, key informants will also be asked about supplementary organizations. Organizations that emerge in interviews in WP3 will be added to the mapping and analysed accordingly.

*Table 2. Potential inclusion and exclusion criteria for sample of organizations that develop and disseminate guidelines for the five priority areas.*

Inclusion criteria	Exclusion criteria
Public sector organisations and/or group of experts that produce clinical guidelines for healthcare professionals commonly involved in the treatment and care of the five disease priority areas.	Professional associations, which exclusively serve as trade unions or for the purpose of accreditation of healthcare professionals.
Professional associations which represent healthcare professionals commonly involved in the treatment and care of the five disease priority areas (including those reported by MS RFI), namely general practitioners, gynaecologists,	Organisations, which disseminate information exclusively at a subnational level (i.e., not for use on national level). This includes for example specific hospital-based prescribing guidelines/formularies. These will only be included when no national level or regional level dissemination is available in the specific country.

 Request for information for EMA commissioned impact research, EMA/234019/2022, EMA Pharmacovigilance Office, 19 May 2022

Inclusion criteria	Exclusion criteria
psychiatrists, neurologists (Valproate) general practitioners, geriatricians, infectiologists, internists, orthopaedist, neurologist, rheumatologist (Fluoroquinolones) dermatologists, gastroenterologists, general practitioners, rheumatologists, (Methotrexate)* general practitioners, endocrinologists (Metformin) oncologists (Fluorouracil and related substances) Nurses Pharmacists	
Organisations based in one of the six countries	

\* It is acknowledged that methotrexate is prescribed by oncologists, however this category of prescribers is less relevant with regards to the implementation of the RMM included in this study.

Third, eligible organizations will be described according to their features, including the type of entity, level of operation and information on publication of clinical guidelines (see coding framework WP1).

## **WP2. Document collection and content analysis of clinical guidelines**

Clinical guidelines will be retrieved through the (healthcare) professional organizations' websites and through a domain-specific query using a proprietary search engine (Google Inc., PubMed) in which active ingredients, class names and indications of use for priority medicines will be used as search strings in combination with terms linked to clinical care e.g., guideline, treatment, care. When guidelines are behind a paywall or access is restricted to members, the issuer will be approached by telephone or e-mail to ask for (free) access. Secondly, all organisations that issue guidelines (WP1) will be contacted to enquire whether they have produced other documents in addition to those retrieved (including prior versions). Key informants will also be asked about supplementary guidelines in interviews (in WP3). Guidelines that emerge in interviews in WP3 will be added to the compilation of guidelines and analysed accordingly.

We will review the clinical guidelines (including versions and timelines for updates) that are (publicly) available on/via the websites of the organizations identified in WP1 to determine which guidance, information and/or recommendations relevant to the five case RMMs are available. While these organisations can provide information on medicine safety in various forms (such as position statements, evidence reviews and commentaries, newsletters, bulletins and educational resources), we will restrict document collection to clinical guidelines (and documents that relate strictly to the development and revision thereof, such as manuals) used in clinical practice as they are generally considered the most authoritative documents for clinical guidance (see definition in WP1 page 15). A search timeframe will be applied based on the timelines indicated for approval dates of the RMM in each Member State (see Appendix II, page 33). The duration of time (number of months) from national implementation to implementation of RMM in clinical guidelines will be determined.

Guidelines will be analysed using a coding framework designed to extract information relevant to the study (see coding framework WP2). An initial coding framework was piloted to ensure scope and applicability. This included a pilot test on a subset of eligible clinical guidelines as well as [review by consortium members and the EMA](#).

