- Inflammatory, autoimmune and cancer diseases/Methotrexate with a measure to prevent dosing errors (2019)(9);
- Chronic disease: Diabetes/Metformin (2016) followed by a measure to monitor kidney function of certain patients (10);
- and Cancer diseases/Fluorouracil and related substances guiding to test for lack of dihydropyrimidine dehydrogenase (DPD) before starting fluorouracil, capecitabine, tegafur or flucytosine by injection or infusion (2020) (11).

An overview of the RMMs for these medicinal products can be found in Appendix I. Since these areas have been subject to prominent post-marketing risk communication, and regard various types of diseases and

therefore diverse healthcare prescribers, they are appropriate to study the diffusion of emergent safety information at national level.

This research, therefore, aims to investigate the role played by national health and regulatory authorities, national clinical guideline developers and (inter)national professional associations or expert groups in a selected group of European countries spread across Europe and with differences in healthcare systems when communicating emerging safety information. We will focus on identifying the networks and channels through which these entities receive and disseminate safety information. We will also identify the key factors (enablers and barriers) influencing how individual entities decide whether safety information is sufficiently serious to act on or disseminate to members and/or the wider public. This includes assessment of the key elements of the risk minimization measure that are included in new or updated clinical guidelines. To explore the variety of diffusion strategies for emergent drug safety information, we will focus on a set of five disease areas and medicines which have been subject to post-marketing risk communication measures. These medicines are prescribed and or dispensed by different types of health care providers, including general practitioners, specialists, nurses and pharmacists. These will be further examined in parallel in six European countries, resulting in 30 case studies (five per country) in total.

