## **WP2. Content analysis of clinical guidelines**

The following information will be registered for identified clinical guidelines:

- **General information** on the clinical guideline (name, version number & version date (national level publication), number & version date (only applicable to international guidelines, international level publication) frequency of updating (number/months), website/link, funding reported to be received (yes/no) and country;
  
- Information about the **target audience** of the guideline (coverage [country, regional, other, not specified], setting [primary care, secondary care, both, other, not specified], and medical specialty [general practitioners, neurologists, psychiatrists, oncologists, orthopaedists, internists, geriatricians, endocrinologists, rheumatologists, dermatologists, gastroenterologists, nurses, pharmacists and others), the **population** to whom the guideline applies (children [0-9 years], adolescents [10-17 years], adult [18-64 years], seniors [65 and older], pregnant females, other), and treatment (active substance: valproate, fluoroquinolones), methotrexate, metformin, fluorouracil and related substances) and **therapeutic area** based on approved indications (neurology, psychiatry, diabetes, infections, immunology, oncology, other);
  
- **Information about the RMM** included in guideline: information on case study medication safety mentioned (yes/no), content of safety information (original language and English translation), RMM mentioned (yes/no, see Appendix I, page 31-32), RMM tool mentioned (yes/no), type of RMM tool (SmPC, package leaflet, visual reminders on packaging, HCP guide/checklist, patient guide, patient card, annual risk acknowledgement form, DHCP, and suspension), recommendations in relation to RMM included (yes/no), clinical action related to RMM (yes/no, see list in Appendix I), explicit mention of reference for RMM information (yes/no), reference (in case explicit mention of reference is yes).

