**Appendix II: Information on approval dates for RMMs received from MS RFI**

Risk minimisation measure	Valproate	(Fluoro-) Quinolones	Methotrexate	Metformin	Fluorouracil & related substances
SmPC updates	DK: Jul 18 GR: Mar 22 LV: Aug-Nov 18 NL: Jul 18 PT: Jun 19 SI: Dec 18	DK: May 19 to Sept 20 GR: Jan 19-Sep 21 LV: Q2 19 NL: Apr 19 to Feb 20 PT: Jun 19 to Jul 20 SI: Apr 19 to Jun 20	DK: Sep 18 to Jul 19/Mar 21 GR: May 19/Apr 20/Jun 21 LV: Jan 20 NL: 20 PT: Jan-Aug 20 SI: Oct 20	DK: May-Dec 17/Nov 19 GR: Oct 20 LV: Q1 17 NL: Dec 16/Jan 17 PT: May 18 SI: Mar 17	
Visual reminder on packaging	DK: Oct 18 GR: May 19 LV: Nov 18-Jan 19 NL: Oct 18 PT: Jun 2019 SI: Dec 18		DK: Sep-Dec 18/Mar 21 GR: Jul 20 LV: Jan 20 NL: Jan 20-Nov 21 PT: Jan-Aug 20 SI: Oct 20		
Healthcare professional guide/checklist	DK: Sep 18 GR: May 19 LV: Nov 18 NL: Nov 18 PT: Nov 18 SI: Nov 18		DK: Mar 20 GR: Jul 20 LV: Sep 19 NL: Oct/Nov 20 PT: Jan20 SI: Mar 21		
Patient card	DK: Sep 18 GR: May 19 LV: Aug-Nov 18 NL: Nov 18 PT: Nov 18 SI: Nov 18		DK: Mar 20 GR: Jul 20 LV: Nov 19 NL: Apr 20 PT: Jan-Aug 20 SI: Oct 20		
Patient guide	DK: Sep 2018 GR: May 19 LV: Nov 18 NL: Nov 18 PT: Nov 18 SI: Nov 18				
Annual risk acknowledgment form	DK: Aug 18 GR: May 19 LV: Nov 18 NL: Nov 18 PT: Nov 18 SI: Nov 18				
Direct HPC (it is noted the DHPCs are disseminated by the marketing authorisation holders, however NCAs	DK: Sep 18 GR: Dec 18 LV: Nov 18 NL: Nov 18 PT: Nov 18 SI: Nov 18	DK: Apr 19 GR: Apr 19 LV: Apr 19 NL: Mar 19 PT: Oct 18 SI: Mar 19	DK: Sep 19 GR: Sep 19 LV: Nov 19 NL: Oct 19 PT: Dec 19 SI: Sep 19		DK: May 20 GR: May 20 LV: Jun 20 NL: May 20 PT: May 20 SI: May 20

could disseminate them further)					
Suspension		DK: - GR: - (susp. 12, NR) LV: - (susp. 19, NR) NL: - (susp. 17, NR) PT: - SI: - (susp. Apr 19, NR)			

\*This table includes the tools for risk minimisation which EMA has considered most relevant to integration in clinical guidelines in their request for information to Member States but does not include a complete list of all RMM tools required by PRAC for the case examples. NR: not registered

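### Time available to take up a risk minimisation measure differs strongly by therapeutic area, so uptake and time to integration are not comparable as planned; between countries this matters only for metformin

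*Protocol*

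**What the plan says.** Section 9.1 (WP2) makes elapsed time an outcome: "The duration of time (number of months) from national implementation to implementation of RMM in clinical guidelines will be determined". Objective 2 in section 8 also names time to integration. Section 9.2.2 says current versions are assessed and elapsed time is noted where possible. Section 9.3 codes "RMM mentioned (yes/no" for each guideline and records its version date. The abstract and the end of section 9.3 plan analysis by country and by therapeutic area.

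The start of observation is tied to national dates: "A search timeframe will be applied based on the timelines indicated for approval dates of the RMM in each Member State". No end date is attached. Figure 1 places document collection in September-October 2022, but WP2 continues: "Guidelines that emerge in interviews in WP3 will be added to the compilation of guidelines and analysed accordingly". Figure 1 runs interviews to February 2023, with an extension in March-April 2023.

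Appendix II gives the national dates. For fluorouracil the Direct Healthcare Professional Communication (DHPC) dates are "DK: May 20 GR: May 20 LV: Jun 20 NL: May 20 PT: May 20 SI: May 20". For metformin, which has only product-information (SmPC) dates, the row includes "GR: Oct 20 LV: Q1 17 NL: Dec 16/Jan 17". Section 9.9 does not list unequal follow-up among the limitations.

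**The concern.** Counting months from each national date aligns the start of observation but not its length. Guidelines are read at roughly one calendar time, so an RMM from 2020 has had far less time to enter a guideline than one from 2016-17. This has two effects:

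- The yes/no coding is read at unequal follow-up, which lowers apparent uptake for recent RMMs.
- Durations are seen only for guidelines that integrated within the window. Slow integrations of recent RMMs have not yet happened and drop out, so recent RMMs look faster.

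The effects point in opposite directions: an area could seem both worse at uptake and quicker at it with no real difference behind either. At stake is the description of differences between therapeutic areas, which informs the enablers and barriers and then the recommendations to regulators under objective 3.

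**Working it through.** **Inputs.** Five RMMs in six countries give 5 × 6 = 30, which agrees with the protocol ("resulting in 30 case studies (five per country) in total"). Start dates are from Appendix II: DHPC for four RMMs, SmPC for metformin. Where a range or several dates are listed, the first is used (Denmark metformin May 2017, Latvia Q1 2017 as January, Netherlands December 2016). The end is October 2022, the last month of document collection in Figure 1. This is an assumption, because the protocol sets no version cut-off.

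**Window.** w = 12 × (2022 − year) + (10 − month). Examples: May 2020 gives 24 + 5 = 29; December 2016 gives 72 − 2 = 70; October 2020 gives 24 + 0 = 24.

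| RMM (start event) | DK | GR | LV | NL | PT | SI |
|---|---|---|---|---|---|---|
| Fluorouracil (DHPC) | 29 | 29 | 28 | 29 | 29 | 29 |
| Methotrexate (DHPC) | 37 | 37 | 35 | 36 | 34 | 37 |
| Fluoroquinolones (DHPC) | 42 | 42 | 42 | 43 | 48 | 43 |
| Valproate (DHPC) | 49 | 46 | 47 | 47 | 47 | 47 |
| Metformin (SmPC) | 65 | 24 | 69 | 70 | 53 | 67 |

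**By area.** Mean windows are 28.8, 36.0, 43.3, 47.2 and 58.0 months in table order.

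**By country.** Over the four DHPC rows the means are DK 157/4 = 39.3, GR 154/4 = 38.5, LV 152/4 = 38.0, NL 155/4 = 38.8, PT 158/4 = 39.5 and SI 156/4 = 39.0. The spread is 1.5 months. With metformin added, Greece falls to 35.6 against 42.2-45.0 elsewhere.

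**Sensitivity.**
- Ending at the 1 March 2023 milestone adds 5 months to every window: fluorouracil 33-34, metformin 58-75 outside Greece and 29 in Greece. The gaps do not change.
- Starting from the first dated tool of any kind gives area means of 28.8, 39.0, 43.8, 48.7 and 58.0 in the same order.
- Starting from the last dated tool, the shortest window is 7 months (valproate SmPC, Greece, March 2022), Danish metformin falls from 65 to 35, and country means run from 17.8 to 42.6.
- A guideline added from an interview in April 2023 could be read 6 months later than one collected in October 2022.

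**Consequence under identical behaviour.** The rates are assumptions; the protocol gives none.
- Fixed revision cycle c, random phase, integration at the next revision: uptake = min(1, w/c); mean observed lag = min(w, c)/2.
- Constant rate with median m: uptake = 1 − 2^(−w/m); mean observed lag = 1/λ − w/(e^(λw) − 1), with λ = ln 2/m.

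| Assumption | Uptake at 24 / 29 / 70 months | Mean observed lag (months) |
|---|---|---|
| Cycle 36 | 0.67 / 0.81 / 1.00 | 12 / 14.5 / 18 |
| Cycle 60 | 0.40 / 0.48 / 1.00 | 12 / 14.5 / 30 |
| Cycle 120 | 0.20 / 0.24 / 0.58 | 12 / 14.5 / 35 |
| Median 24 | 0.50 / 0.57 / 0.87 | 10.6 / 12.5 / 23.9 |
| Median 36 | 0.37 / 0.43 / 0.74 | 11.1 / 13.2 / 27.4 |
| Median 60 | 0.24 / 0.28 / 0.55 | 11.4 / 13.7 / 30.3 |

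With a cycle of 24 months or less, every window above gives uptake 1.00 and the same mean lag, so there is no artefact.

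**With a common horizon h.** Every case has the same expected uptake. At h = 24 it is 24/60 = 0.40 (cycle 60) or 0.37 (median 36). With Greek metformin shown apart, the shortest window is 28 months, giving 28/60 = 0.47 or 1 − 2^(−28/36) = 0.42.

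**The case against.** The strongest case on the other side has four parts.

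- **It belongs in an analysis plan.** Horizons, cut-offs and handling of non-events are often left there, and section 9.6 mentions countries' analysis plans. The mere absence of a horizon would not be a finding. But the protocol itself fixes the duration, the reading of current versions and the contrasts, and a version cut-off governs collection by six national teams.
- **The study is descriptive.** "The multiple case studies are descriptive in scope and provide means for initial exploration". No test or rate comparison is specified, section 9.7 grades extent of coverage, and enablers and barriers come chiefly from interviews. This limits the harm to misread descriptive contrasts, which still feed the recommendations.
- **The alternative explanation is collected.** Updating frequency, update cycle and time of validity are recorded. They help explain why an RMM is absent but do not correct truncated durations.
- **The size rests on invented cycles.** This stands. Regulatory communications may also trigger off-cycle updates, and the artefact is small if nearly all or almost no guidelines update within about 24 months.

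A reader might infer that all 30 cases spread over 24 to 70 months, so that country contrasts in general are distorted. The documents do not support that. Both ends of that range are metformin SmPC dates, while the other four RMMs are dated by DHPC and span 28-49 months. Without metformin, country means differ by 1.5 months. Nor is the point independent of the start event: section 9.2.2 also speaks of publication of the RMM, and a single EU date per RMM would equalise windows across countries. Only the inequality between areas would remain.

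**Conclusion.** The point holds for therapeutic areas. To October 2022, fluorouracil has 28-29 months of follow-up against 53-70 for metformin outside Greece, with the other three RMMs between. The gap does not depend on the assumed end date. For countries it is material only for metformin, mainly Greece at 24 months, if these start dates are used; starting from the last dated tool would widen it.

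The direction is clear while integration is incomplete: recent RMMs may appear less often integrated, and faster when integrated. The size is not known. Under the assumed rates above, the uptake gap between 29 and 70 months runs from 0.19 (cycle 36) to 0.52 (cycle 60), and it vanishes with cycles of 24 months or less. It would be too strong to say that false differences will appear. What can be said is that, as planned, a real difference between areas cannot be told from one due to follow-up. The protocol should be changed before areas are compared.

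**What to change.** In sections 9.1 (WP2) and 9.7:

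1. Choose one start event first, and reconcile the WP2 wording (national implementation) with section 9.2.2 (publication of the RMM).
2. Set one version cut-off date for all guidelines, including those added from interviews.
3. Report each guideline without the RMM as *not integrated after n months*, beside the durations.
4. Do not compare durations among integrators only.
5. Where version dates allow, compare therapeutic areas (and countries for metformin) on integration within a common horizon, set by the shortest window on the chosen start event. Show Greek metformin separately if it would otherwise set the horizon. On the dates used here that gives 28 months rather than 24.

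In section 9.9, list unequal follow-up by RMM as a limitation.

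The cost is protocol wording and a derived follow-up time for each guideline. Version dates are already recorded and prior versions already requested. There are two downsides. Late integrations of older RMMs fall outside the common-horizon comparison and are only described. A current version that contains the RMM does not show when it first entered, so guidelines without retrievable prior versions cannot always be dated and should be counted as such.
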